**Mitigating ethnic disparities in access and engagement in spine pain rehabilitation –
STEPPT Mixed Methods Pilot Study**

NCT06835439

(May 23, 2025)

Study Objectives

The purpose of this pilot study is to assess the feasibility, acceptability, and preliminary effectiveness of the STEPPT intervention to improve ethnic disparities in physical therapy referral and adherence between Hispanic and Non-Hispanic White patients with spine pain. We expect the intervention will be feasible and acceptable, with suggested modifications from patient and clinic staff stakeholders that will inform a larger clinical trial. Compared to standard care, we expect STEPPT to reduce ethnic disparities in physical therapy referral and adherence outcomes.

Design & Methods

STEPPT is a health system, quality improvement intervention. Our research team developed the preliminary STEPPT intervention based on available evidence, to promote physical therapy referral and attendance for Hispanic patients with spine pain. Our team then adapted the STEPPT intervention based on insights gained from feedback from Federally Qualified Health Center (FQHC) administrators and co-development workshops conducted with FQHC clinic directors, primary care physicians, nurses, medical assistants, and patient health navigators. The pilot single-arm clinical trial will allow our research team to implement and assess the adapted STEPPT intervention in a single FQHC clinic prior to initiating a larger clinical trial.

Participant Eligibility and Enrollment

Because this is a health system quality improvement intervention, all patients at the FQHC pilot clinic will be included in the study if they: (1) are 18 years of age or older, (2) identify as Hispanic or Non-Hispanic White ethnicity/race, (3) have signed a broad consent for use of de-identified health information for research, and (4a) identify a new spine pain problem at a visit with a primary care physician (new diagnosis of neck or back pain added to the problem list during the visit) OR (4b) have an existing spine pain problem (existing diagnosis of neck or back pain on the problem list) and their physician generates any referral for the spine problem at the visit. Patients with a possible non-musculoskeletal etiology for spine pain (e.g. infection, cancer, urological disorder, pregnancy) or conditions requiring urgent medical intervention (e.g. fracture, cauda equina syndrome) will be excluded.

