Physical Therapy Referral and Adherence Rates (Primary)

The primary outcomes that will be gathered from the electronic health record (EHR) are rates of physician referral to physical therapy (within 3 months of index visit) and patient adherence to physical therapy referral (within 6 months of referral) for spine pain before (3-month baseline) and after (3-month intervention) implementation of STEPPT. Patient sociodemographic characteristics will also be collected from the EHR for descriptive purposes.

Involvement Rating

During STEPPT intervention, a formal process evaluation also will be conducted by the study team to assess clinic involvement in STEPPT training and implementation activities. The study team will conduct monthly audits including reviews of data from all levels of the STEPPT program, and structured observations of the clinic workflow. Process evaluation measures will include a quantitative Involvement Rating Score (range 0 to 11 points, with higher scores indicating greater involvement in STEPPT implementation), supplemented by the qualitative analysis of structured observations and field notes. Based on this evaluation, the research team will provide monthly feedback to clinic staff, which will include a summary report of progress toward equitable rates of physical therapy referral

and adherence. Research staff will support uptake and adherence to STEPPT with regular outreach to FQHC clinic staff to share lessons learned, help problem-solve barriers, and suggest customized strategies.

Patient Interviews

The study team will conduct post-intervention interviews with a subsample of participants to evaluate acceptability and feasibility of the STEPPT intervention. A semi-structured interview guide with open-ended questions was developed using the Reach, Effectiveness, Adoption, Implementation, and Maintenance (RE-AIM) Framework. The interview guide includes questions regarding Hispanic patients' opinions of the materials they received during the pilot intervention, the delivery of the materials, and their experience receiving Enhanced Care Navigation. Interviews will take approximately one hour and will be conducted in the patient's preferred language by trained moderators.

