Interviews will be audio-recorded and transcribed for qualitative analysis. Patient recommendations identified in the interviews will inform the need for additional adaptations before finalizing the STEPPT intervention procedures and materials prior to a larger clinical trial.

Data Processing and Storage: All participant data will be retained in the password-protected, HIPAA-compliant FQHC system. Power BI will be used to extract participant data from EHR and referral systems, and a registry will be used to track participants for enhanced care navigation. Only research team members who are employees or onboarded volunteers at the FQHC, and who have met all HIPAA and patient privacy training requirements, will have access to these data. When participant data are exported from the FQHC system for analysis, data will be coded by an FQHC Data Scientist using a unique identifier such that only deidentified data will be shared and used for analysis. De-identified data that is shared will be stored on password-protected HIPAA-compliant servers at San Diego State University. A Data and Safety Monitoring Plan will be implemented to maintain the safety and confidentiality of all study participants and to ensure data integrity.

Statistical Analysis Plan

The primary outcome of interest is the change in rates of referral and adherence to physical therapy before and after the STEPPT intervention between Hispanic and NHW participants with spine pain, which will define the overall effect of STEPPT on ethnic disparities. Descriptive statistics will be summarized at each time point (baseline vs. intervention) separately for each group (Hispanic vs. NHW). Effect size estimates for change in referral

and adherence rates before and after intervention will be calculated to conduct a power analysis for a larger clinical trial of the STEPPT intervention.

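### No adjustment is planned for case-mix change between periods, so a shift that differs by ethnicity in size or impact would be read as a STEPPT effect

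*Combined protocol and SAP*

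**What the plan says.** Design & Methods describes the study as single-arm: "The pilot single-arm clinical trial will allow our research team to implement and assess the adapted STEPPT intervention in a single FQHC clinic". Under Outcomes, the primary rates are compared "before (3-month baseline) and after (3-month intervention) implementation of STEPPT", and the same paragraph ends: "Patient sociodemographic characteristics will also be collected from the EHR for descriptive purposes".

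The Statistical Analysis Plan sets the primary contrast as the change "before and after the STEPPT intervention between Hispanic and NHW participants with spine pain", and says of this contrast: "which will define the overall effect of STEPPT on ethnic disparities". This is a difference-in-differences, although the plan does not use that term. The only method named is: "Descriptive statistics will be summarized at each time point (baseline vs. intervention) separately for each group (Hispanic vs. NHW"). Effect sizes have one stated use, and the sentence about them ends: "and adherence rates before and after intervention will be calculated to conduct a power analysis for a larger clinical trial of the STEPPT intervention". No regression, weighting, standardisation or balance check is mentioned, and no effect scale is fixed.

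Under Participant Eligibility and Enrollment, patients enter by one of two routes. Under 4a they "identify a new spine pain problem at a visit with a primary care physician"; under 4b they have an existing problem and the physician makes some referral for it.

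**The concern.** Patients are not allocated to period, so the two cohorts may differ in age, sex, preferred language, pain region, or the balance of new and existing problems. If such a difference arises in one ethnic group and not the other, the rates in that group move for reasons unrelated to STEPPT. The planned contrast would count that movement as a change in disparity, in either direction.

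The pilot plans no hypothesis test, so no false claim of significance is at stake. What is at stake is the effect size that the Statistical Analysis Plan hands to the larger trial. If it is inflated, that trial is undersized; if it is deflated, that trial is larger than needed or looks not worth running.

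**Working it through.** The documents give no rates, cell sizes, case-mix data or effect size, so there is no figure of the plan's own to reproduce. All values below are assumptions chosen to show how the bias behaves.

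**Set-up.** Take one binary case-mix factor and no true STEPPT effect. Cell rate = rate without the factor + (share with the factor) × (rate gap). Then:

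bias in the difference-in-differences = (Hispanic shift × Hispanic gap) − (NHW shift × NHW gap)

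**Results for a shift from 40% to 55% (15 points).** The rate without the factor is 30% (40% for NHW in the last column).

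| Rate gap | Both groups shift, equal gap | Only Hispanic patients shift | Both shift, gap halved in NHW |
|---|---|---|---|
| 10 points | 0.0 | +1.5 | +0.75 |
| 20 points | 0.0 | +3.0 | +1.5 |
| 30 points | 0.0 | +4.5 | +2.25 |
| 40 points | 0.0 | +6.0 | +3.0 |

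Worked row, 30-point gap: the Hispanic rate goes from 0.30 + 0.40 × 0.30 = 42.0% to 0.30 + 0.55 × 0.30 = 46.5%. If NHW stays at 42.0%, the contrast is +4.5 points. Standardising both periods to the baseline mix returns it to 0.0. For Hispanic-only shifts of 5, 10 and 20 points, the bias across the same gaps is 0.5 to 2.0, 1.0 to 4.0 and 2.0 to 8.0 points.

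**Scale.** Let a common 40% to 55% shift act on Hispanic rates of 20%/50% and NHW rates of 40%/70%. The cells are 32.0% to 36.5% and 52.0% to 56.5%. The risk-difference contrast is 4.5 − 4.5 = 0, but the ratio of risk ratios is (36.5/32.0)/(56.5/52.0) = 1.05 and the ratio of odds ratios is 1.02. Cancellation therefore depends on a scale that the plan does not fix.

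**New versus existing problems.** Suppose the Hispanic share with a new problem moves from 60% to 70%.
- At assumed intervention-period rates of 80% (new) and 50% (existing): 0.6 × 0.8 + 0.4 × 0.5 = 68%, and 0.7 × 0.8 + 0.3 × 0.5 = 71%, so +3 points.
- At assumed baseline rates of 30% and 50%: 0.6 × 0.3 + 0.4 × 0.5 = 38%, and 0.7 × 0.3 + 0.3 × 0.5 = 36%, so −2 points.

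The sign can thus go either way. A 10-point move is within chance variation: the standard error of the change in share, √(2 × 0.6 × 0.4/n), is about 10, 7 and 5 points for 50, 100 and 200 patients per cell.

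**Effect on the later trial.** With a common rate of 0.40, two-sided 5% alpha, 80% power and no clustering, n per cell = (1.96 + 0.84)² × 4 × 0.40 × 0.60 / d². For d = 10 points, n = 754; for d = 14.5 points, n = 359. A trial of 359 per cell has about 49% power if the true value is 10 points.

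**The case against.** A reader might infer that any shift in case mix between periods biases the primary result. The documents do not support that. NHW patients at the same clinic are a concurrent comparator, and the first column of the table shows a common shift with equal impact cancelling on the risk-difference scale. Such a shift distorts only within-group changes, which the effect-size sentence may also cover.

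A reader might also take the two cohorts to be wholly different patients. The documents do not say so: entry is by visit, and route 4b could bring a baseline patient back.

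Nor does the plan exclude every covariate. Only sociodemographic data are assigned to description. On pain region and new/existing status the plan is silent, and it never states that effect sizes will be unadjusted. Describing patients by period and group might well make sociodemographic shifts visible. That stands, but seeing a shift does not correct the estimate.

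The most substantive objection is that adjustment can remove part of the effect. Both entry routes depend on clinician behaviour (adding a diagnosis, making a referral), and STEPPT trains providers and gives monthly feedback. The new/existing mix may therefore respond to the intervention. Adherence is defined on the referral, and auto-referral changes who is referred. This stands, and it limits the remedy.

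Finally, in the new/existing example mix accounts for 3 of the 33 points between 38% and 71%. The 95% half-width of an unadjusted contrast, 1.96 × √(4 × 0.24/n), is about 27, 19 and 14 points for 50, 100 and 200 per cell. Sampling error may well exceed this bias. That lowers the priority, but a confidence interval does not allow for bias.

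**Conclusion.** The point holds in a limited form. The plan names no adjustment for case-mix change between periods, reserves sociodemographic data for description, and treats the resulting contrast as the effect of STEPPT. Bias arises if the shift differs by ethnicity, if the factor's impact differs by ethnicity, or if a ratio scale is used.

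Under the assumptions above, a 15-point shift gives about 0.75 to 6 points, and shifts of 5 to 20 points in Hispanic patients only give 0.5 to 8 points. Whether any such shift will occur cannot be judged from the documents. For a pilot without a planned test this is a moderate matter, worth correcting because the estimate is the stated input to the next trial's power analysis.

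**What to change.** - Tabulate case mix in the four period-by-ethnicity cells: age, sex, preferred language, pain region and new/existing status.
- Beside the crude rates, report a difference-in-differences on the risk-difference scale with a 95% CI. Adjust it, or standardise each ethnic group to its own baseline distribution, using age, sex, preferred language and pain region from the EHR. Standardising within group leaves the baseline disparity intact.
- Show new (4a) versus existing (4b) status as a separate stratified or sensitivity analysis, with a note that STEPPT may itself change this mix.
- Report adherence among referred patients and also among all eligible patients.
- State how a patient who qualifies in both periods is counted.
- Give the power analysis both the crude and the adjusted estimates, with their intervals.

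The cost is a little more analysis on data drawn from the EHR. Adjusted estimates may be unstable if the 3-month cells are small, so the covariate list should be short and fixed in advance.

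### The larger trial is to be powered on effect estimates from a one-clinic pilot, with no interval, target difference or clinic-level variance named

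*Combined protocol and SAP*

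**What the plan says.** The Statistical Analysis Plan section defines the primary outcome as the "change in rates of referral and adherence to physical therapy before and after the STEPPT intervention between Hispanic and NHW participants with spine pain". It then promises descriptive summaries by period and ethnic group, and says that estimated effects on referral and "adherence rates before and after intervention will be calculated to conduct a power analysis for a larger clinical trial". That is the whole of the plan for sizing the next study. No interval, minimum important difference, intraclass correlation or sensitivity range is mentioned, and no alpha, power or expected rate is given.

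Design & Methods says the pilot will "assess the adapted STEPPT intervention in a single FQHC clinic prior to initiating a larger clinical trial". The Outcomes section compares rates "before (3-month baseline) and after (3-month intervention) implementation of STEPPT", with referral counted up to 3 months after the index visit and adherence up to 6 months after referral. Participant Eligibility and Enrollment states no sample size: "all patients at the FQHC pilot clinic will be included in the study if they" meet the listed criteria.

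**The concern.** Study Objectives says the pilot is to inform a larger trial, and the effect-size sentence is the only quantitative route to it. Two things go wrong if the sentence is followed as written.

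First, required sample size varies with the inverse square of the assumed effect. A pilot estimate that is high by chance therefore gives a larger trial that is much too small, and one that is low by chance gives a trial that is needlessly large. Without an interval, the reader cannot see which is plausible.

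Second, STEPPT works through record-system rules, staff training and clinic workflow. A larger trial may well allocate whole clinics. Its size would then depend on how much clinics differ, which one clinic cannot show.

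**Working it through.** **1. Inputs.** From the documents: one clinic; one 3-month baseline and one 3-month intervention period; an outcome that contrasts change between Hispanic and NHW patients. Not stated: patient numbers, ethnic split, rates, alpha, power, intraclass correlation. There is no figure of the plan's own to reproduce, so the sizes below rest on stated assumptions.

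**2. What needs no assumption.** Between-clinic variance has (clinics − 1) degrees of freedom, here 1 − 1 = 0. With a single before/after contrast, any drift peculiar to this clinic and these months that affects the two ethnic groups differently cannot be separated from the effect. Recruiting more patients changes neither fact.

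**3. Precision of the disparity estimate.** Take four independent proportions, one per ethnic group and period:

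SE = √[Σ p(1 − p)/n]

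Assume rates near 50%, so p(1 − p) = 0.25, and a true contrast of 15 points.

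- 100 Hispanic and 40 NHW per period: SE = √(2 × 0.25/100 + 2 × 0.25/40) = √(0.005 + 0.0125) = 0.132. 95% of estimates lie within 15 ± 1.96 × 13.2, about −11 to +41 points. P(estimate ≤ 0) = Φ(−15/13.2) = 13%. P(estimate ≥ 22.5) = 1 − Φ(7.5/13.2) = 29%.
- 400 and 160 per period: SE = √(0.00125 + 0.003125) = 0.066. 95% of estimates lie between about +2 and +28 points. P(estimate ≤ 0) = Φ(−15/6.6) = 1%. P(estimate ≥ 22.5) = 1 − Φ(7.5/6.6) = 13%.

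**4. Effect on the next trial.** Suppose it is sized for 80% power, two-sided 5%, at 22.5 points (1.5 times the truth). It would have (15/22.5)² = 44% of the size needed. Its power at 15 points is 1 − Φ(1.96 − 2.80 × 15/22.5) = 1 − Φ(0.09) = 46%.

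**5. A second set of assumptions.** Assume referral rising from 30% to 45% in Hispanic patients and from 40% to 45% in NHW patients (true contrast 15 − 5 = 10 points), with 70% Hispanic. The true requirement, ignoring clustering, is 7.85 × [(0.21 + 0.2475)/0.7 + (0.24 + 0.2475)/0.3]/0.10² ≈ 1,789 patients per period. In 200,000 simulated pilots per row, each used to plan the next trial from its point estimate:

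| Pilot patients per period | 95% half-width, referral (points) | Estimate ≤ 0 | Planned size per period, 10th to 90th percentile* | True power below 50%* |
|---|---|---|---|---|
| 200 | ±21 | 18% | 285 to 18,280 | 42% |
| 800 | ±10 | 3% | 622 to 11,547 | 22% |
| 1,600 | ±7 | 0.4% | 811 to 6,569 | 13% |

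*Among pilots with a positive estimate.

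If adherence is counted only among referred patients, and is assumed to go from 40% to 55% (Hispanic) and from 50% to 55% (NHW), the half-widths are ±34, ±17 and ±12 points. All these figures count patient sampling error only.

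**6. Clustering.** For a simple comparison of rates between clinics, the multiplier on sample size is 1 + (m − 1) × ICC. With an assumed 100 patients per clinic, an ICC of 0.01 gives 1 + 99 × 0.01 = 1.99, and 0.10 gives 1 + 99 × 0.10 = 10.9. For a within-clinic ethnic gap, clinic effects shared by both groups cancel, and what matters is how the gap and its change vary between clinics. One clinic informs neither quantity.

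**The case against.** The strongest reply is that imprecision cannot be proved from the documents. They give no expected numbers, and a large clinic would yield a usable referral estimate. This stands in part: at 1,600 patients per period the half-width for referral falls to ±7 points. Adherence remains at ±12, and no number of patients supplies the missing clinic-level variance.

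It can also be said that the larger trial is not yet written, that clustering belongs in its own protocol, and that the plan nowhere says pilot estimates will be the only input or that clinic variance will be left out. That is fair. Allocation by clinic is an inference from the level at which STEPPT is delivered. But the plan names no other input, and this is the place to name them.

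Estimating effects in a pilot is legitimate, and Study Objectives lists preliminary effectiveness. The weakness is in using the point estimate to set sample size, not in reporting it.

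Three stronger readings are tempting, and the documents do not support them.

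- *The comparison is uncontrolled.* Standard Care Control names a control condition, and during the intervention NHW patients receive neither the tailored education package nor enhanced navigation. The control is weak, because it is non-randomised and NHW patients with a new spine problem also get the auto-referral, but it exists.
- *The effect size is for the wrong estimand.* The effect-size sentence mentions only change before and after, but the same paragraph defines the outcome as a contrast between ethnic groups. The wording is ambiguous, no more. The ambiguity is still worth closing: with 100 and 40 patients, the variance of the contrast (0.0175) is 3.5 times that of the change in Hispanic patients alone (0.005).
- *A low estimate would stop the programme.* There is no go/no-go rule in the documents.

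**Conclusion.** The concern holds as a planning weakness. It is not an arithmetic error, and it does not threaten the pilot's validity for feasibility and acceptability. It should be changed.

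That one clinic and one before/after contrast cannot supply between-clinic or clinic-by-period variance follows from the design and is certain. That the disparity estimate is too imprecise to size a trial is likely but conditional. It rests on assumed rates, ethnic split and numbers, and it weakens for referral as the clinic gets larger. Across the two assumed sizes in step 3, the chance of an estimate at least half as large again as the truth is 29% or 13%, and acting on an estimate 1.5 times the truth leaves the larger trial at about 46% power in place of 80%.

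**What to change.** Amend the last sentence of the Statistical Analysis Plan section as follows.

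1. Keep the effect estimates. State that the effect is the difference in differences (Hispanic change minus NHW change), estimated separately for referral and for adherence, each with a 95% confidence interval.
2. State that the larger trial will be powered on a pre-stated smallest worthwhile reduction in the absolute gap, not on the pilot's point estimate. The pilot supplies the baseline rate in each ethnic group and the flow of eligible patients, each with a 95% interval.
3. State that, if the larger trial is allocated by clinic, the intraclass correlation will come from outside the pilot, for example from routine data of other clinics, or that the sample size will be shown over a range of values.

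The cost is SAP wording and a little extra analysis; conduct of the pilot does not change. Data from other clinics may need separate approval, because the waiver in the Informed Consent section was granted for the pilot and is limited to patients who signed the broad consent. The range in item 3 is the fallback. The planned larger trial may come out bigger.
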